11.2 CHU-9D

Completed by: parent/carer of CYP with constipation

Ages: Designed for ages 7+ but used for all participants.

Versions: Proxy version

Scoring criteria: 9 questions with different weights; no missing data allowed.

11.3 Tracer condition analysis – Primary parental outcome – WEMWBS

Warwick Edinburgh Mental Wellbeing Scale

Version: 14-item scale (long version)

Scoring: 14 items, scored 1 to 5 on likert scale, for total score range 14-70.

Missing data: Mean of completed items used as the value for the missing responses, for maximum of 3 missing items.

11.4 Mental health and wellbeing - Strengths and Difficulties Questionnaire (SDQ)

Completed by: all

Versions: Ages 2-4 (MedSciNet study database), 4-17 (Health Check Portal & MedSciNet study database); At baseline everyone does the age 4-17 version in the Health Check/Portal (which is

only slightly different than the age 2-4 version). Questionnaire differences (Age 2-4 vs Age 4-17):

1. Often argumentative with adults → Often lies or cheats
2. Can stop and think things out before acting → Thinks things out before acting
3. Can be spiteful to others → Steals from home, school, or elsewhere

3-part likert scale, 25 items (5 items in each of 5 subscales), each item scored 0-2

Outcomes:

- Total difficulties score (20 items; excludes prosocial subscale)
- 5 subscale scores: Emotional, conduct, hyperactivity, peer, prosocial
- Externalizing score (conduct and hyperactivity) and Internalizing score (emotional and peer)

Missing items – For any of the 5 sub-scales, if at least 3 of 5 items are completed then the scores can be scaled up pro rata. If any of the sub-scales is missing 3 or more items, the Total Difficulties score will not be calculated.

SDQ impact

4-part likert scale, 5 items, scores 0-10

2 age versions – 4-17 on portal (baselines), 2-4 and 4-17 on MedSciNet (follow-up); one minor difference: classroom learning → learning.

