8.2 Health Service Use Tracer condition populations

Subset of populations in section 8.1, excluding those without a tracer condition (asthma, constipation, or eczema).

Definition of tracer condition: Uses the same methodology applied by the CYPHP call/recall system, i.e. diagnosis, disease management, or therapy codes in the primary care record, and age restrictions. The clinical (Read/SNOMED) codes and therapies are listed in Appendix. For all conditions, an individual's complete records are interrogated.

If a subject meets the call/recall criteria for a tracer condition, they are defined as having a tracer condition from the first recorded event used in the definition (e.g. if they are defined as having asthma due to having an asthma diagnosis or three prescriptions of asthma medication in one year, we define their asthma 'start date' as the date of the first of those prescriptions or diagnosis).

We treat all conditions as ongoing, i.e. the observation period is continuous from the 'start date' of their condition (described above) until their observation 'end date' which occurs when they leave a GP practice, turn 16 years of age, or reach the end of the study period.

➤ Randomised HSU Tracer condition population

Intervention and control only, *excluding* pilot clusters

Subpopulations:

- Asthma
- Eczema
- Constipation

➤ Quasi-experimental HSU Tracer condition population

Intervention, control *and* pilot clusters

Subpopulations:

- Asthma
- Eczema
- Constipation

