8.4 Consented tracer condition population

Inclusion criteria:

- Aged 0-15 (<16) years
 - Age at date of consent
- Registered with a Southwark or Lambeth GP practice included in the trial.
 - Registration at time of consent
- Parental informed consent confirmed

➤ Randomised consented population

Intervention and control only, *excluding* pilot clusters

Subpopulations:

- Asthma
- Eczema
- Constipation

➤ Quasi-experimental consented population

Intervention, control *and* pilot clusters

Subpopulations:

- Asthma
- Eczema
- Constipation

Note: Self-report of tracer condition by parent/carer/CYP is acceptable. We will not confirm these against primary care data.

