11. PARTICIPANT-REPORTED OUTCOME DEFINITIONS AND ANALYSIS METHODS

11.1 Tracer condition analysis – Primary child outcome – PedsQL

The Pediatric Quality of Life Inventory (PedsQL) is a brief measure of health-related quality of life in children and young people. This will be completed at baseline and each follow up. In all instances, the outcome for analysis will be parent-reported and child-related. However, where appropriate, child-reported outcomes will also be collected and reported.

Age versions: 0-12 months, 13-24 months, 2-4 years, 5-7 years, 8-12 years, 13-18 years

For 0-12 months and 13-24 months:

Subscales: Physical Functioning, Physical Symptoms, Emotional Functioning, Social Functioning, Cognitive Functioning

Summary scores: Physical health summary score (mean of physical functioning and physical symptoms), Psychosocial Health (mean of emotional, social, and cognitive scales), Total Score (mean of all scales)

For age 2+:

Subscales: Physical functioning, Emotional functioning, Social functioning, School functioning

Summary scores: Physical health summary score, Psychosocial Health (mean of emotional, social, and school scales), Total Score (mean of all scales)

Mismatch of questionnaire version and participant age: Treat as missing any questionnaires for ages 8+ completed by children age 0-4 at baseline.

Total score: Sum of items divided by the number of items answered for all scales.

- Items: There are 21-45 items in the PedsQL, depending on age of CYP; each item assigned value of 0, 25, 50, 75, 100.
- Missing data: use the mean value for items within the subscale. If more than 50% missing in a subscale, exclude the participant's data.

To combine data across ages:

- Check distribution of scores; transform if needed.
- Convert scores to z-scores (number of SDs above/below the trial mean).
- Analyse follow-up z-score, adjusted for baseline z-score for individuals.

Primary Outcome: Total Score at 6-month follow-up

Secondary outcomes from PedsQL: Physical Health score, Psychosocial Health score, same analysis method.

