11.5 Asthma severity - Asthma Control test

Completed by: parent/carer of CYP with asthma

Version: Adult 12-60+

Scoring criteria: 5 items on 5 part likert scale, each scored 1-5, for a total score 5-25. No missing data allowed.

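### SDQ under age 2, CHU-9D under 7 and the Asthma Control Test under 12 are analysed outside the age range the SAP records, with no age-restricted estimate planned

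*SAP*

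**What the plan says.** SAP section 8.4 defines the consented population as "Aged 0-15 (<16) years", with age taken at consent. Very young children are expected, since section 11.1 lists PedsQL forms for 0-12 and for 13-24 months.

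For the three instruments at issue:

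- **CHU-9D (11.2):** "Ages: Designed for ages 7+ but used for all participants".
- **ACT (11.5):** one form only, "Version: Adult 12-60" and upwards, answered by the parent or carer of a child with asthma.
- **SDQ (11.4):** completed by all participants. "Versions: Ages 2-4 (MedSciNet study database), 4-17 (Health Check Portal & MedSciNet study database"). "At baseline everyone does the age 4-17 version in the Health Check/Portal". The section calls the two forms only slightly different and lists three changed items out of 25.

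Section 11.9 gives one random-effects regression approach for the questionnaires at 6 and 12 months. Age group and the baseline score are among the covariates. It states no age restriction and no age-specific estimate. Section 15 carries the same scores into the equity interaction models.

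**The concern.** The SAP records a lower age limit for each instrument, then uses the instrument below that limit without saying how the resulting scores are to be read. A treatment effect from all ages together averages children for whom the form was made with children for whom, on the SAP's own description, it was not. If the second group's scores respond less to a real change in health, the average understates the effect in the first group, and a null result cannot be told apart from a form that did not fit. If the analyst notices this only at analysis, any age cut-off would be chosen with the data in view.

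At stake are the conclusions on child mental health, health utility and asthma control. All three are secondary outcomes.

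**Working it through.** The SAP gives no sample size, power or age distribution for these instruments, so there is no planned figure to reproduce. Its one questionnaire sample size is for PedsQL and does not enter here.

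**Step 1: ages outside the recorded range.** The population covers 16 single years of age (0 to 15). With a lower limit of L years, the share of the age range below it is L/16.

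| Instrument | Lower limit (source) | Share of age range below it |
|---|---|---|
| SDQ, any form | 2 (11.4) | 2/16 = 12.5% |
| CHU-9D | 7 (11.2) | 7/16 = 44% |
| ACT | 12 (11.5) | 12/16 = 75% |

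These are shares of the age range. They become shares of participants only if ages are spread evenly, which the SAP does not say.

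**Step 2: what the age covariate does.** In the section 11.9 model, age group shifts the expected score for each age band. The arm effect remains a single coefficient averaged over all bands. Adjustment therefore deals with differences in level by age. It does not make a score valid where the form does not apply, and it does not show whether the effect differs in and out of range.

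**Step 3: dilution.** Let f be the fraction of analysed children in range and r the effect in out-of-range scores divided by the effect in in-range scores. With equal variances,

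pooled effect / in-range effect = f + (1 − f) × r.

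Neither f nor r is in the SAP. Purely as an illustration, with evenly spread ages:

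| Instrument | f | r = 0 | r = 0.5 | r = 1 |
|---|---|---|---|---|
| SDQ (under 2 out) | 0.875 | 0.875 | 0.94 | 1 |
| CHU-9D | 0.5625 | 0.56 | 0.78 | 1 |
| ACT | 0.25 | 0.25 | 0.625 | 1 |

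The result runs from no dilution to a large one, depending on r alone. The plan as written would not reveal which applies.

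**Step 4: SDQ at ages 2-3.** These children (another 2/16 of the age range) complete the 4-17 form at baseline, while a 2-4 form is held in the study database used at follow-up. The difference is 3 of 25 items, one of them a rewording. The mismatched form supplies only the baseline covariate. A weaker covariate costs some precision and does not bias a randomised comparison, so this is minor.

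**Step 5: bias between arms.** Both arms use the same forms and scoring, and children in both arms develop over the same interval. Nothing in the passages makes the misfit differ by arm.

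**The case against.** **Age is already adjusted for, and all three outcomes are secondary.** Both are true. The first removes level differences but not the validity question (step 2). The second limits the weight of the point.

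**The SDQ sentence about baseline is harmless.** Largely so. A reader might infer from it that the whole SDQ analysis rests on a misfitting form. The SAP does not support that, because a 2-4 form exists for follow-up and the baseline score is only a covariate. What stands is that no form covers a child under 2. The SAP's remark that the versions differ slightly compares 4-17 with 2-4 and says nothing about infants. The missing-item rule removes some of these children, since a subscale missing three or more items blocks the total score. But subscales with at least three of five items answered can be scaled up, so a score can still result.

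**PedsQL shows that the SAP has an age policy and then ignores it.** This is also tempting and goes too far. The PedsQL rule, "Treat as missing any questionnaires for ages 8+ completed by children age 0-4 at baseline", corrects one gross wrong-form error where a suitable form existed. It is not a general rule on age validity.

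**The asthma population may not reach down to infancy.** Section 8.2 refers to "therapy codes in the primary care record, and age restrictions", and the details sit in a file not shown. That could narrow the ACT range. However, section 8.2 concerns the health service use population. For the consented population, section 8.4 gives 0-15 years with "Note: Self-report of tracer condition by parent/carer/CYP is acceptable" and no check against primary care data.

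**CHU-9D may be handled in the economic analysis plan.** Section 1.2 says that plan is a separate document, and it may set an age rule for QALYs. It would not settle how section 11.2 and the equity models in section 15 use the score.

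**Conclusion.** The point holds as a modest one. CHU-9D, ACT and, for children under 2, the SDQ are analysed below the ages the SAP itself records, with no age-restricted estimate to help interpret the pooled effect. The expected harm is dilution and unclear meaning, not bias between arms. NEA, PedsQL and WEMWBS are untouched.

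The size cannot be stated. A reader might infer that the ACT effect shrinks by 75% and the CHU-9D effect by 44%. That would need ages spread evenly over 0-15 and no response at all in out-of-range scores. The SAP supports neither assumption, and nothing in it suggests that a parent's report of asthma control in, say, a 10-year-old is wholly unresponsive. Only the shares of the age range (2/16, 7/16, 12/16) follow from the text.

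**What to change.** In the SAP, before analysis and using age at baseline throughout:

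- **11.4 (SDQ):** restrict SDQ analyses, including those in section 15, to children aged 2 or over at baseline. No special handling is needed at ages 2-3.
- **11.2 (CHU-9D):** keep the all-age analysis and pre-specify an estimate in children aged 7 or over. Section 11.2 also names only carers of children with constipation as respondents, while the same section and Table 1 have CHU-9D used for all participants; reconcile this in the same edit.
- **11.5 (ACT):** keep the all-age analysis. Pre-specify the estimate at ages 12-15, show under-12s separately, and fit an arm-by-age-band term.
- **Reporting:** state beside each all-age CHU-9D and ACT result that it includes ages outside the instrument's recorded range.

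The cost is SAP wording and age filters on data already collected. The restricted estimates will be less precise, and the ACT 12-15 group may be small. The SDQ rule also drops some children who turn 2 before follow-up, in exchange for a rule fixed on a characteristic that treatment cannot change.

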21. DATA QUALITY AND MISSING DATA

Data cleaning methods will be described in the Data Management Plan.

Consenting participants completing the trial:

We will report the number of participants providing data at the 6 month and 12 month follow-up time points:

 x out of N (y%) continued participating in the trial up to z-month follow up, where N is the number consented.

The numbers withdrawing and lost to follow-up will also be reported.

Questionnaire data completeness:

Data completeness in terms of return rate will be summarised, by frequency and proportion of forms returned (observed) out of those expected.

We will assess all questionnaires to look for missing items. Data completeness will be assessed and summarised with completion rates for baseline demographics and each questionnaire at both time points reported. This will help to identify any potential bias in the completion of follow-up data.

We may also present this split by cluster and other stratification factors if missing data is excessive (>20%).

Missing data assumptions:

1. Initially all analyses will be performed on complete cases, under the assumption of missing completely at random.

2. Where data is >5% missing, multiple imputation may be conducted, and would be the preferred method for treating missing data. This assumes data is missing at random (weaker assumption than missing completely at random).

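### Read as written, the SDQ missing-item rule voids the Total Difficulties score when three or more prosocial items are missing, although that score contains no prosocial items

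*SAP*

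**What the plan says.** Four statements in SAP section 11.4 matter here.

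- Structure of the instrument: "3-part likert scale, 25 items (5 items in each of 5 subscales), each item scored 0-2".
- Subscales reported: "5 subscale scores: Emotional, conduct, hyperactivity, peer, prosocial".
- Composition of the summary score: "Total difficulties score (20 items; excludes prosocial subscale".
- Missing items, in two consecutive sentences: "For any of the 5 sub-scales, if at least 3 of 5 items are completed then the scores can be scaled up pro rata", and then "If any of the sub-scales is missing 3 or more items, the Total Difficulties score will not be calculated".

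The section also lists an externalizing and an internalizing score, each made of two subscales, and gives no missing-item rule for either.

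Two later sections determine what happens to a form without a score. Section 11.9 puts the individual baseline questionnaire score, and its cluster mean, among the covariates for the 6-month and 12-month analyses. Section 21 says: "Initially all analyses will be performed on complete cases, under the assumption of missing completely at random". Multiple imputation is optional there, for data with more than 5% missing.

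**The concern.** A missing-item rule should depend only on the items that enter the score. Here the definition of Total Difficulties leaves the prosocial subscale out, but the rule for declaring the score missing does not. If the scoring code follows the text, some fully observed scores are thrown away and nothing is gained in exchange.

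The loss is not confined to the form concerned. The baseline score is a covariate, so a child whose follow-up form is complete can still drop out of the complete-case model because of prosocial items left blank at baseline. The cluster-mean baseline covariate would also rest on fewer children. Section 15 uses the SDQ again in the equity models.

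The rule should also have only one reading. One programmer may test five subscales and another four, and they would then analyse different sets of children.

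**Working it through.** **1. Reproduce the plan's item count.** Five subscales of five items give 5 × 5 = 25 items. Without the five prosocial items, 25 − 5 = 20, which is the figure in section 11.4. Prosocial items therefore contribute nothing to Total Difficulties.

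**2. Compare the two rules on every pattern.** Each subscale can have 0 to 5 items missing, which gives 6^5 = 7,776 patterns of missing counts. A subscale is scorable with 0, 1 or 2 missing.

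- Rule as written (all five subscales must be scorable): 3^5 = 243 patterns keep the score and 7,776 − 243 = 7,533 lose it.
- Rule limited to the four contributing subscales: 3^4 × 6 = 486 keep it and 7,776 − 486 = 7,290 lose it.
- Difference: 7,533 − 7,290 = 243 patterns. In all of them only the prosocial subscale fails.

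This shows that the two rules differ. It does not show how often, because the patterns are not equally likely.

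**3. Size under an assumed item-missing rate.** The SAP gives no rate, so let each item be missing independently with probability q. The chance that one subscale lacks three or more items is

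p = 10q³(1 − q)² + 5q⁴(1 − q) + q⁵.

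The share of forms discarded is 1 − (1 − p)^5 as written and 1 − (1 − p)^4 under the four-subscale rule. The extra loss is p(1 − p)^4.

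| q (assumed) | p | Discarded, as written | Discarded, four subscales | Extra loss per form |
|---|---|---|---|---|
| 1% | 0.00001 | 0.005% | 0.004% | 0.001% |
| 5% | 0.00116 | 0.58% | 0.46% | 0.12% |
| 10% | 0.00856 | 4.2% | 3.4% | 0.83% |
| 20% | 0.05792 | 25.8% | 21.2% | 4.6% |

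**4. From forms to children.** A follow-up analysis adjusted for baseline needs two scored forms per child. If the two forms are also independent, the extra share of children lost is (1 − p)^8 × [1 − (1 − p)²]. Section 5.1 plans for 2,012 children with 30% loss to follow-up, so 2,012 × 0.7 ≈ 1,408 complete. The extra loss is then:

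- q = 1%: 0.002%, fewer than one child.
- q = 5%: 0.23%, about 3 children.
- q = 10%: 1.6%, about 22 children.
- q = 20%: 7.0%, about 98 children. At this rate the four-subscale rule already loses 1 − (1 − p)^8 = 38% of children, so the prosocial clause would not be the main difficulty.

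If the same children leave items blank on both forms, these figures fall.

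**The case against.** The strongest defence concerns the reading. The first sentence of the rule says five subscales. The second, about Total Difficulties, does not repeat the number, and the definition a few lines above has already excluded prosocial. An analyst summing four subscales might apply the rule to those four. That reading is possible, and the authors may have intended it. It is not the natural one, because the subscales just named are all five and no other section narrows the term. Even if it was intended, the text should say so.

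It can also be said that section 21 names multiple imputation as the preferred method once more than 5% is missing. That step is optional, and imputing a score that was fully observed does not repair the scoring rule.

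A reader might infer more than the SAP supports, in four ways.

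- *That any incomplete subscale voids the score.* It does not. A subscale with one or two items missing is scaled up; the trigger is three or more of five.
- *That several per cent of children will be lost.* Under independence, an extra loss of 1% to 3% per form needs roughly 11% to 16% of all items missing, and the four-subscale rule would then itself discard about 4% to 13% of forms. Nothing in the SAP points to such a rate, or to prosocial items being skipped as a block.
- *That the loss falls on the youngest children.* Section 11.4 says that everyone completes the version for ages 4-17 at baseline, so skipping related to age is conceivable. The SAP does not report it.
- *That the main SDQ result is at risk.* Section 11.4 does not rank the SDQ scores.

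**Conclusion.** The point holds as a defect of wording with a small practical effect. The missing-item rule in section 11.4 does not fit the section's own definition of Total Difficulties and, followed as written, discards scores that were fully observed. This conclusion rests on the text alone and needs no assumed rate.

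The size does rest on assumptions: independent item missingness at a rate the SAP does not give. At 5% or below the extra loss is negligible. It becomes noticeable at 10% and above, or if prosocial items are left blank together. No primary outcome is affected, since sections 9.1 and 9.3 name non-elective admissions, PedsQL and WEMWBS. Bias between the arms has not been shown. The change is worth making because it is easy, not because a result depends on it.

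**What to change.** Replace the second sentence of the rule with: *If any of the four difficulties subscales (emotional, conduct, hyperactivity, peer) is missing 3 or more items, Total Difficulties will not be calculated; missing prosocial items affect only the prosocial score.*

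Optionally, add that the externalizing score depends only on the conduct and hyperactivity subscales, and the internalizing score only on the emotional and peer subscales, since the section states no rule for either.

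The cost is one or two sentences, made before the scoring code is final. It needs no new data, and the loss rule for the four contributing subscales stays as it is.

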11.5 Asthma severity - Asthma Control test

Completed by: parent/carer of CYP with asthma

Version: Adult 12-60+

Scoring criteria: 5 items on 5 part likert scale, each scored 1-5, for a total score 5-25. No missing data allowed.

11.6 Eczema severity - Patient Oriented Eczema Measure

Completed by: parent/carer of CYP with eczema

Version: Children (proxy completion version)

7 items on 5-part likert scale, score 0-28. Maximum of one item missing, and assigned score 0.

